1 BACKGROUND

1.1 THE ADVERSE IMPACT OF SEVERE PNEUMONIA ON CHILD HEALTH IN AFRICA

Community-acquired pneumonia (CAP) is common and remains associated with substantial morbidity and mortality, especially in lower and middle-income countries (LMIC) [1]. In 2016, 1 per 1000 children younger than 5 years of age was estimated to die due to pneumonia globally [2, 3]. In Africa, pneumonia incidence is estimated at one episode per 3 child-years in young children and severe pneumonia has a mortality of 10-15% [1, 4, 5]. While the proportion of childhood deaths attributable to pneumonia decreased in the 1990s, this has since remained at 18% [6]. Many children with pneumonia in LMIC require inpatient management. In Malawi, 36% of 1-5 year-olds presenting with pneumonia were admitted to hospital and a quarter of these suffered from very severe pneumonia (according to pre-2012 World Health Organisation (WHO) definitions) [5]. In Papua New Guinea the mortality of severe pneumonia requiring hospitalisation was 6%, but another 7% were readmitted with severe pneumonia within 1 month of discharge [7]. In Zambia, the mortality of severe pneumonia managed in hospital was recently estimated at 18% [8]. An overall 5% out-of-hospital mortality has been reported for children discharged in Uganda after inpatient management of an infection, with children of mothers with a lower level of education at much higher risk of death after discharge [9].

The UNICEF and WHO Global Action Plan for prevention and control of pneumonia (GAPP) data [10], indicates that care-seeking of under-fives with pneumonia symptoms in countries represented in PediCAP is relatively high (South Africa 88%, Uganda 80%, Zambia 70%, Zimbabwe 59%). In 2015, high mortality rates from pneumonia were still observed despite improvements since the early 2000s (South Africa 7/1000 live births, Uganda 8.6/1000, Zambia 9.8/1000, and Zimbabwe 10.2/1000) [2]. Correspondingly, acute respiratory infections account for 17% of under-five deaths in South Africa, 16% in Uganda, 14% in Zambia and 15% in Zimbabwe [2]. No robust data are available comparing hospitalisation rates and outcomes across African countries.

The costs associated with inpatient care for severe childhood pneumonia in LMIC are themselves substantial, estimated at up to US\$600 per episode [7]. An early intravenous to oral switch of antibiotics is known to reduce episode costs by around 40% in high-income settings [11], without compromising efficacy.

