9.2.2 SECONDARY OUTCOME MEASURES

Efficacy/effectiveness secondary outcomes (assessed in all children) are:

- Proportion of children experiencing CAP-related readmission to hospital or CAP-related death within 28 days post-randomisation (CAP-relatedness adjudicated by the independent Endpoint Review Committee)
- Length of stay required during the index hospitalisation (days) (excluding any additional day remaining in hospital solely for the purpose of trial-related pharmacokinetic studies, see [Section 10.1](#)), and total days of stay in hospital up to 28 days
- Proportion of children dying within 28 days post-randomisation (all-cause mortality)
- Total days of supplemental oxygen during index hospitalisation
- Total days of antibiotic exposure during 28 days post-randomisation, including antibiotics received during the initial hospitalisation and antibiotics self-reported by parents/carers at follow-up visits
- Proportion of children requiring modification of randomised antibiotics for any reason other than early stopping, or requiring a subsequent course of antibiotics for any reason up to 28 days (also considered as separate components)
- Proportion of children requiring modification of randomised antibiotics for inadequate response, or additional courses in the index hospitalisation for CAP relapse

Safety secondary outcomes (assessed in all children) are the proportion of children:

- Experiencing SAEs, including hospital-acquired infections

- Experiencing grade 3 or 4 adverse events
- Experiencing antibiotic-related adverse events
- Experiencing key solicited events (reflecting common drug toxicities), specifically diarrhoea, vomiting and gastrointestinal disorders, skin rashes, thrush/candida
- Modifying antibiotics for antibiotic-related adverse events (i.e. toxicity)
- Experiencing specified clinical complications including sepsis, lung abscess, empyema
- Experiencing line complications (complications related to IV access)

Note that by definition a hospital-acquired infection prolongs hospitalisation so is an SAE following [Section 7](#). Therefore, the SAE secondary endpoint will include all hospital-acquired infections.

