- initial IV regimen (benzylpenicillin plus gentamicin or ampicillin plus gentamicin, vs benzylpenicillin or ampicillin alone, vs ceftriaxone alone or cefotaxime alone)
- prior oral/intramuscular antibiotics before hospitalisation for the index CAP episode
- baseline CRP (semi-quantitative, 10-40 vs 40-80 vs >80 mg/l)
- chest X-ray features (abnormal vs normal vs uninterpretable vs not done based on any chest X-ray up to and including 72h from admission).

Secondary outcome analyses will similarly use exact tests and binomial regression for binary outcomes, and t-tests and normal linear regression (potentially on transformed data depending on the observed data distribution, adjusted for baseline values) for continuous outcomes. Ranksum tests will be used if there is gross departure from normality that cannot be adequately addressed by data transformation. Adverse events will be summarised by body system.

A Statistical Analysis Plan will be written and approved by the Trial Management Group (TMG), Trial Steering Committee (TSC) and the DMC before the first interim analysis is reviewed by the DMC.

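### Section 9.5 names tests for hospital stay, oxygen days and antibiotic days without saying how deaths are counted; applied as written, they can favour an arm with more early in-hospital deaths

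*Protocol*

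**What the plan says.** Protocol section 9.5 assigns continuous secondary outcomes to "t-tests and normal linear regression (potentially on transformed data depending on the observed data distribution, adjusted for baseline values) for continuous outcomes". The fallback is: "Ranksum tests will be used if there is gross departure from normality that cannot be adequately addressed by data transformation". The same section makes all randomised children the primary analysis population and introduces the secondary analyses as following the primary approach.

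The continuous outcomes in the secondary list of section 9.2.2 are all day counts after randomisation:

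- index stay: "Length of stay required during the index hospitalisation (days" (the unit is days);
- overall stay: "total days of stay in hospital up to 28 days";
- oxygen: "Total days of supplemental oxygen during index hospitalisation";
- antibiotics: "Total days of antibiotic exposure during 28 days post-randomisation".

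Section 9.2.2 excludes from length of stay any extra day spent in hospital only for pharmacokinetic sampling, so it does define what counts as a day of stay. Neither 9.2.2 nor 9.5 says how a child who dies enters any of these four outcomes. All-cause mortality at 28 days is a separate secondary outcome, and death is part of the primary endpoint.

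**The concern.** A day count that stops at death cannot tell a fast recovery from an early death: a child discharged on day 2 and a child who dies on day 2 both contribute two days. The named tests read both as short stays.

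The protocol treats short durations as benefit. The co-primary duration objective in section 1.5 includes keeping hospital stay short, and section 6.6 lists length of stay and oxygen duration among the efficacy measures. Section 1.1 does not suggest that deaths are negligible: for Africa it states that "severe pneumonia has a mortality of 10-15" per cent, and it quotes 6% and 18% for hospitalised children in two other settings. If one arm loses more children early, its stay and oxygen results can look better for that reason alone.

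A smaller point concerns the baseline clause. None of the four durations has a value before randomisation, so the clause cannot be applied to them literally.

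**Working it through.** The protocol gives no figure of its own here to reproduce, and it gives no mean, SD, time of death or arm-specific mortality. The inputs below are therefore assumptions.

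**Assumed inputs.** Stay in survivors is identical in both arms, with mean μ = 5 days (7 as the alternative) and SD 3. Section 1.4.4 gives only a modal stay of 4 days. Children who die have mean duration d and SD 1. There are 500 children per arm, as in the amoxicillin v co-amoxiclav comparison of section 9.3.1.

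**Shift in the mean.** With mortality m, the arm mean is (1−m)μ + m·d. The difference between arms is therefore Δm × (d − μ).

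- Each percentage point of excess mortality, with μ = 5 and d = 2: 0.01 × (2 − 5) = −0.03 day.
- Δm of 1 to 6 points, d from 1 to 4 days and μ from 4 to 7 days: from 0 (0.06 × (4 − 4)) to −0.36 day (0.06 × (1 − 7)).

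**Rejection rate with no true effect in survivors.** The arm variance is (1−m)·9 + m·1 + m(1−m)(μ − d)².

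Worked case, μ = 5, mortality 10% v 6%:

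- Deaths on day 2. Means 4.70 and 4.82, difference −0.12. Variances 9.01 and 9.03. SE = √((9.01 + 9.03)/500) = 0.190. z = −0.63. Two-sided rejection 9.7%.
- Deaths on day 4. Means 4.90 and 4.94, difference −0.04. Variances 8.29 and 8.58. SE 0.184. z = −0.22. Two-sided rejection 5.5%.
- Deaths on day 5. No shift, rejection 5%.

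Other cases by the same formula:

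| Mortality | μ | Deaths on day | Difference (days) | Two-sided rejection |
|---|---|---|---|---|
| 10% v 6% | 7 | 2 | −0.20 | 16.8% |
| 10% v 6% | 7 | 4 | −0.12 | 9.7% |
| 7.5% v 4.5% | 5 | 2 | −0.09 | 7.6% |
| 7.5% v 4.5% | 5 | 4 | −0.03 | 5.3% |
| equal | any | any | 0 | 5% |

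**Does the rank-sum fallback help?** A simulation used 475 per arm, gamma-distributed stays (mean 5, SD 3) and stays cut at a death time with mean day 2. Two-sided rejection was:

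| Mortality | t-test | Rank-sum |
|---|---|---|
| 3% v 3% | 5.2% | 5.3% |
| 6% v 3% | 7.5% | 8.6% |
| 9% v 3% | 17.1% | 22.2% |

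The excess t-test rejections almost all favour the arm with more deaths. Ranking does not help, because an early death still receives one of the best ranks.

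**The case against.** The strongest reply is that section 9.5 is labelled brief and leaves detail to a full statistical analysis plan, where the handling of deaths would normally be settled. That is right as far as it goes. A reader might infer that the plan has decided to count deaths as short durations; the protocol does not say so, and is silent on worst rank, exclusion and competing events alike. But 9.5 does more than defer. It names the test family, and none of the named tests deals with death unless the outcome itself is redefined.

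Second, the bias is conditional. It needs a mortality difference and deaths earlier than the usual stay. Children step down only after at least 24 hours of intravenous treatment and clinical improvement (sections 5.2.1 and 5.2.2), and the duration groups do not diverge by design before day 4. Deaths caused by the randomised options may therefore come later, often after discharge. Those do not shorten index stay or oxygen days, and a late in-hospital death can lengthen stay. This stands, and it is why the day-4 results matter as much as the day-2 results.

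Third, it is tempting to use 15% v 9% as the mortality contrast. In section 9.3.1 these are planning rates for readmission or death combined, so using them as mortality leaves no room for readmissions. Section 3.2 also excludes children expected to need ventilation or intensive care, which makes the background mortality an uncertain guide.

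Fourth, a reader might conclude that the cost analysis is distorted too. It is not: section 10.3 costs each group up to death or day 28, so days actually used are the correct input, and deaths enter through years of life lost.

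Finally, mortality is reported separately. That helps interpretation but does not correct the duration tests.

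**Conclusion.** The point holds in conditional form. The protocol pairs outcomes that death cuts short with tests that ignore death, and gives no rule for deaths. If all randomised children are analysed as written and one arm has more early in-hospital deaths, the comparison can favour that arm. The documents do not support saying that it will.

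Under the assumptions shown, the shift is about 0 to 0.36 day. For stay with a survivor mean of 5 days and 10% v 6% mortality, two-sided rejection runs from about 5.5% (day-4 deaths) to about 10% (day-2 deaths). Equal mortality gives no bias. The primary endpoint is untouched.

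The baseline clause is a wording flaw, not a demonstrated analysis error. It is written for continuous outcomes in general and could suit measures that have a baseline sample, such as the carriage changes in section 9.2.3.

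**What to change.** In section 9.5, and in step in the statistical analysis plan:

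1. **Hospital stay and oxygen duration.** Use a method that does not reward death. One option is days alive and out of hospital, and days alive and off oxygen, to day 28, with death as the worst value, analysed by a site-stratified rank method or an ordinal model. The other is time to discharge alive or to oxygen weaning, with death as a competing event, so that a child who dies counts as never discharged or weaned and is not simply censored. Adjust for site and the other randomisation, as in the primary analysis.
2. **Total antibiotic days.** Report these as an exposure measure beside mortality, with a summary in survivors or per day alive. A death-penalised version is debatable for an exposure measure and is not needed.
3. **Costing.** Keep actual days used.
4. **Baseline clause.** Limit it to outcomes that have a baseline measurement.

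The cost is a change of wording; dates of death, discharge and oxygen use in the index admission are already needed for the existing outcomes. The drawback is units slightly less familiar than mean days, which can be offset by showing mean days descriptively.

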10 ANCILLARY STUDIES

10.1 PHARMACOKINETIC SUBSTUDIES

The aim of the PK substudies with PediCAP-A and PediCAP-B is to characterise the PK of oral amoxicillin and clavulanate (clavulanic acid) in the PediCAP population. Since clavulanic acid is not expected to affect amoxicillin PK, the model developed will be used to infer expected amoxicillin exposure in all children receiving oral step-down the main trial. Very little oral absorption data on clavulanic acid has been published in children, and hence the investigation of 7:1, 4:1 and 14:1 ratios will enable estimation of clavulanic acid oral absorption and dose linearity.

The overall objectives of the nested PK substudies are therefore to develop a PK model of amoxicillin and clavulanic acid from which the PK of the whole PediCAP population can be inferred, and to investigate clavulanic acid linearity across 4:1, 7:1 and 14:1 ratio formulations.

These objectives will be achieved by PK sampling in two groups of children.

10.1.1 PHARMACOKINETIC SAMPLING IN CHILDREN RANDOMISED IN THE MAIN TRIAL (PEDI CAP-A)

A subset of children joining the main trial (PediCAP-A) will be approached for additional written informed consent to take part in a PK substudy of the 7:1 co-amoxiclav formulation if they are randomised to oral co-amoxiclav step-down. In total, 60 children with a complete set of PK samples (defined below) will be included (out of the total 500 randomised to 7:1 co-amoxiclav in PediCAP-A), targeting a minimum of 6 children per weight-band from 6kg up to 25kg to ensure a minimum dataset is generated for each proposed dose in the main weight range.

PK sampling will occur immediately before and then after the first morning dose and will consist of 5 samples per child weighing 6kg or more (2ml per sample); e.g. before observed dosing (5-10 min pre-dose), during early absorption (0.25-1h post dose), around the expected C_{max} (1-2h), during early disposition (2-6h), and in the terminal phase (6-12h). Optimal design and model-based stochastic simulation-estimation will be used to determine the exact sampling windows (which will maximise the information obtained from sampling compared to fixed sampling times) and the allocation of children between the weight-bands, while keeping the total pre-specified sample size. Allowable blood draws are 10ml or more in unwell children weighing 5kg or more ([Appendix II](#)): any child weighing less than 5kg will have one (4kg) or two (3kg) of the 5 PK samples dropped (chosen according to the optimal design) and will be considered to have a complete PK sample set (leading to total blood draws over 12h of 8ml and 6ml respectively). A cannula will be used to avoid repeated venepuncture, and anaesthetic cream to numb the child's skin.

Any child consenting to the PK substudy who does not have the complete set of PK samples taken for any reason (e.g. refusal of later samples) will be replaced, to give a total of 60 children with a complete set of PK samples. PK data from samples from any children not providing the full set will nonetheless be pooled for the model-based analysis (see below). For some children, this may require a short period of additional hospitalisation (e.g. if they would otherwise have been discharged mid-morning, but need to stay until the evening for the final PK sample), which will be clearly explained to each parent/carer, has been costed as part of the trial, and will not contribute to the trial secondary endpoint, length-of-stay. Parents/carers will be given travel money for the extra PK day.

10.1.2 PARALLEL PHASE II PHARMACOKINETIC TRIAL (PEDI CAP-B)

An additional, but separate, 120 children meeting the same eligibility criteria as for the main trial ([Section 3](#)) will undergo randomisation to two different co-amoxiclav formulation strengths, 4:1 vs

14:1 in a parallel Phase II PK trial (PediCAP-B), and all 120 will undergo intensive PK sampling exactly as described in [Section 10.1.1](#) above.

Randomisation (stratified by weight band) will continue until 60 children with complete PK samples (as defined above) have been enrolled for each formulation strength. As for the 7:1 formulation, PK data from samples from any children not providing the full set will nonetheless be pooled for the model-based analysis.

10.1.3 ASSAYS AND ANALYSIS

Samples will be shipped to a central laboratory in the UK for processing. The PK MOP contains full details of PK procedures and sample handling, including storing plasma aliquots separately for shipping. Plasma concentrations will be determined with highly-sensitive LC-MS/MS methods.

A population PK model will be developed to identify and quantify the effect of covariates including body size (e.g. weight), age, renal function, HIV infection/exposure status, and malnutrition. Secondary PK outcomes (area under the time-concentration curve, maximum and minimum concentration, time to maximum concentration) will be derived from the model and compared across weight-bands using geometric means and geometric mean ratios. Models will then be extended to include information on the different strengths, and in particular associations with side-effects (e.g. intensity and severity of diarrhoea) will be estimated for the different formulation strengths. All data manipulations and model post-processing will be done in R (version 3.4 or higher) [56] and the PK model will be produced in NONMEM version 7.4 or higher.

No formal power calculation has been performed. Based on previous studies, 60 evaluable children in each formulation group should be sufficient to assess the association between normalised dose and area under the curve of clavulanic acid. Since population pharmacokinetic analysis will be performed, it has also been shown that approximately 50 children in total are required to detect most clinically meaningful covariate effects (in this case whether clavulanic acid PK are linear). Hence, with 60 children per group, this substudy should be adequately powered to identify important predictors of both amoxicillin and clavulanate exposure, particularly the impact of malnutrition/under-nourishment.

The population PK model will enable us to predict the PK of all 1220 children and conduct population dose-response modelling (PK-pharmacodynamic (PK-PD) model) In particular, we will investigate associations between trial primary and secondary outcomes and simulated time above the minimum inhibitory concentration (MIC), the key target for beta-lactam antibiotics. We will also use the PK model together with dosing and covariates information, to simulate expected PK profiles and calculate the probability of target attainment in this population under any given dose.

10.2 MICROBIOLOGICAL SUBSTUDY

The primary objective of the microbiological substudy is to evaluate the impact of amoxicillin and co-amoxiclav oral treatment and the duration of hospitalisation and of antibiotic treatment on prevalence and resistance of pathogens causing CAP, and on the carriage of multidrug-resistant Gram-negative bacteria (MDR-GNB) in children, in comparison with continuous IV treatment. A secondary objective is to assess the dynamics of the causative pathogens and their underlying resistance mechanisms under and following therapy. The goal is to answer in depth questions regarding the potential impact of antibiotic management strategies on antimicrobial resistance by using novel microbiological methods to determine how these strategies relate to resistance in colonizing bacteria. Recognizing the serious threat of antibacterial resistance to future African child health, this will enable outcomes beyond the immediate health benefits of narrower compared to

broader-spectrum antibiotics to be taken into account in clinical decision-making about antibiotic treatment strategies in children initially managed in hospital for severe pneumonia in sub-Saharan Africa.

66 children randomised in each site (total 330) will be approached for consent for microbiological characterisation of the commensal nasopharyngeal and faecal flora through nasopharyngeal and peri-rectal sampling (or faecal sampling from a child wearing a nappy, or who passes a stool). Children in the microbiological substudy will also be asked to provide peri-rectal swabs at discharge and at the week 4 face-to-face follow-up (or samples from nappy/passed stool as above). Each child will also provide one additional nasopharyngeal swab after trial entry, at either discharge or week 4 (determined by an additional randomisation to ensure comparability). Only two nasopharyngeal samples are collected because these are more invasive for the child than peri-rectal/faecal sampling. Randomisation between discharge and week 4 for the second nasopharyngeal swab will ensure that changes in nasal flora can be assessed unbiasedly at both timepoints, without requiring three swabs per child.

A MOP will guide participating laboratories in the processes of sample collection and management locally, and in order to optimise and standardise local procedures. The manual will include detailed instructions on sampling, transport and storage of study samples and strains, and will be made available online and through written materials. Training will be provided for PIs and other key local personnel from participating clinical sites to ensure optimal and standardised sampling from all participating children including quality assurance exercises and quality control. The samples will be stored at -80°C for batched transfer to the University of Antwerp for analysis. Strain types and resistance genes of isolated bacteria will be further investigated.

Briefly, peri-rectal and nasopharyngeal swabs will be transferred frozen at -80°C, and then be thawed and processed at the University of Antwerp. Total bacterial DNA will be extracted from uncultured swab samples following standard procedures, and shotgun sequenced using Illumina technology. We will determine species and functional richness and diversity and determine phylogenetic and functional composition of the metagenome. As a complementary methodology to the functional screen mentioned above, we will also mine the nasopharyngeal and gut microbiome for known antibiotic resistance genes, as well as further investigate those that have detected in the functional screen. Based upon a manually compiled list of target resistance genes, hidden Markov models will be built and used to screen the nasopharyngeal and gastrointestinal metagenomes generated within this project. This will allow the quantification of different resistance pools in the paediatric population, and the impact of antibiotic management strategies and hospitalisation on amplification of these pools.

